In a recent study, it was shown that a cohort of AD patients without systemic insulin resistance, pSer312-IRS-1 was positively associated with MRI atrophy, whereas p-PanY-IRS-1 was negatively associated with it, in a highly characteristic pattern of regions. The significance of this regional pattern lies in its spatial correlation with the normal IRS-1 brain expression. It is speculated that neuronal-enriched plasma EVs containing IRS-1 may be preferentially derived from brain regions with high levels of IRS-1 expression. Therefore, the IRS-1 phosphorylation pattern seen in these EVs may reflect its phosphorylation status in specific brain regions that suffer brain atrophy in early AD in association with higher burden of brain insulin resistance. These findings provide hope that using these biomarkers may also possibly demonstrate target engagement and follow response to treatment in clinical trials that aim to reverse brain insulin resistance (e.g. liraglutide).

In summary, there is mounting evidence that PD pathogenesis is accelerated by brain insulin resistance and that liraglutide can markedly reduce this abnormality, thereby reducing the motor and non-motor symptoms of the disorder.

SPECIFIC OBJECTIVES:

The primary objective of this clinical trial is to test the therapeutic efficacy and safety of liraglutide treatment of patients with idiopathic PD. The secondary objective is to correlate the magnitude of any observed therapeutic efficacy with degree of reduction in peripheral insulin resistance over the course of drug treatment.

RESEARCH DESIGN AND METHODS:

Study Hypotheses: We hypothesize that global disease status (MDS-UPDRS) and especially cognition in PD patients will improve significantly by the end of daily liraglutide treatment for one year compared to those treated only with the placebo (i.e., drug vehicle). We also hypothesize that the improvement seen in each patient will be proportional to the degree of improvement in peripheral as well as neuronal insulin resistance seen in the treatment period.

Endpoints: The primary outcomes are measures of the drug's effects on motor (assessed by MDS-UPDRS III) and non-motor symptoms of PD (assessed by NMSS and MDRS-2) after 52 weeks of treatment at full tolerated dose. The secondary outcomes are measures of the association between liraglutide's effects on peripheral insulin resistance, markers of insulin resistance on plasma EVs enriched for neuronal origin, PD symptoms and safety.

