Study Type: This is a phase II, randomized, double-blinded, placebo-controlled clinical trial.

STUDY POPULATION:

Cases: Fifty-seven patients with a diagnosis of idiopathic PD will be recruited and randomized to receive once daily self-administered injections of liraglutide (1.2 or 1.8 mg, as tolerated) or placebo at the same dose range in a 2:1 study design.

Inclusion Criteria:

- Diagnosis of idiopathic PD according to the United Kingdom Parkinson's Disease Society Brain Bank (UKPDSBB) criteria^a for at least 2 years, and/or a DaT-confirmed diagnosis of PD
- Responsive to levodopa or dopaminergic treatment
- Male or female between 25 and 85 years of age at time of enrollment
 - Women of child-bearing potential (WOCBP) must agree to use a reliable method of contraception (e.g., oral contraceptive or long-term injectable or implantable hormonal contraceptive, double barrier methods (such as condom plus diaphragm, condom plus spermicide foam, condom plus sponge), or intra-uterine devices) throughout the duration of the trial period and must have a negative serum pregnancy test at screening
 - Male patients with female partners who have child bearing potential must agree to use adequate contraception throughout the duration of the trial period

- Capacity to give informed consent
- Ability to self-administer, or to arrange a care partner to administer trial drug, to comply with trial protocol, and to attend necessary clinic visits off medication

a: Note: the study team will not consider the UKPDSBB criterion “more than one affected relative” as exclusionary. According to the scientific community, family history is not regarded as exclusionary and this specific criterion is no longer used (reference).

Exclusion Criteria:

- Diagnosis or suspicion of other causes for Parkinsonism, including drug- or toxin-induced parkinsonism and other neurodegenerative conditions, including multiple system atrophy, progressive supranuclear palsy, Huntington's disease, Wilson's disease, or Alzheimer's disease
- Active treatment with anticholinergic medications (e.g., trixyphenidil or tricyclic antidepressants)
- Known abnormality on CT or MRI brain imaging considered to cause symptoms or signs of neurological dysfunction, or considered likely to compromise compliance with trial protocol
- Concurrent dementia defined by a score lower than 120 on the MDRS-2 and/or inability to complete scale per neuropsychologist’s discretion

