Sample Size Calculation: This is a randomized, double-blinded, placebo-controlled clinical trial that aims to evaluate the effects of liraglutide on motor and non-motor symptoms in patients diagnosed with PD. The primary outcome of this study will be the difference in MDRS-2 scores at baseline and follow-up (52 weeks after titration) between the active and placebo control group. The power analysis was performed utilizing data reported in a previous study using a similar GLP-1 agonist (**Table 1**). While score changes associated with active medication were not compared to a placebo group but to a cohort of patients treated with “conventional PD medication”, this data represent the closest approximation available for power analysis and sample size calculation.

With a total of 57 patients (38 in the drug group and 19 in the placebo group), the study will have an 82.7% chance of rejecting the null hypothesis of equal means, assuming an average critical difference of 5.1 points on the MDRS-2 and a standard deviation of 6.4 for the drug group and 5.3 for the placebo group with a significance level (alpha) of 0.050 using a two-sided two-sample unequal-variance t-test.

This sample allows for a 12% dropout of up to 6 subjects (e.g., if they are diagnosed with T2D during the course of the study) and still maintain 81.3% power with a total of 51 patients (i.e., 36 cases in the drug group and 15 cases in the placebo group). If the rate of drop out is higher than anticipated, the study will enroll and randomize additional subjects; subjects will be enrolled/randomized in multiples of 3 subjects in order to maintain the 2:1 randomization. The additional enrolled subjects will aim to maintain the power of the study. In total, up to 63 patients will be enrolled and randomized. No more than 42 patients, including drop outs, will be exposed to the drug during the trial.

Statistical Methods: The analysis populations for this study are defined as:

1. Full Analysis Set (FAS): all randomized subjects who receive at least one dose of study drug and have a baseline and at least one post-baseline efficacy score (MDRS-2 and MDS-UPDRS).
2. Per-Protocol (PP) population: a subset of the FAS population, excluding subjects with major deviations from the protocol that may substantially affect the results of the primary efficacy analysis.
3. Safety population: all randomized subjects who receive at least one dose of study drug.

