The final determination of protocol violations, and therefore the composition of the PP population, will be made prior to unblinding the database and will be documented separately. Analysis of all efficacy

Table 1 (from Aviles-Olmos et al., 2013⁵¹)

Changes in the score on LED, dyskinesia rating scale, Mattis DRS-2, MADRS, and PDQ39 summary index between baseline and month 14

	Baseline	6 months	12 months	Difference, baseline to 12 months	14 months	Difference, baseline to 14 months
	Mean (SD)	Mean (SD)	Mean (SD)	Mean (SD); 95% CI	Mean (SD)	Mean (SD); 95% CI
LED						
Exenatide	973 (454)	1011 (518)	997 (446)	24.3 (123.6); -37, 78	1015 (467)	42.3 (137); -22, 107
Conventional PD medication	977 (493)	1061 (613)	1121 (620)	143.7 (223.6); 49, 238	1125 (638)	148.0 (232); 50, 246
Dyskinesia rating scale, on medication						
Exenatide	2.3 (2.8)	2.5 (4.1)	3.3 (4.5)	1.0 (4.2); -1.0, 3.0	3.2 (4.0)	1.0 (3.8); -0.8, 2.7
Conventional PD medication	2.6 (2.9)	3.5 (3.9)	2.5 (2.7)	-0.04 (2.7); -1.2, 1.1	2.7 (3.5)	0.1 (4.3); -1.7, 1.9
MATTIS DRS-2						
Exenatide	140.1 (7.7)	142.4 (2.3)	142.3 (2.5)	2.2 (6.4); -0.8, 5.2	142.9 (2.0)	2.8 (6.0); -0.1, 5.6
Conventional PD medication	139.5 (4.5)	138.2 (5.1)	136.6 (6.1)	-2.8 (5.3); -0.6, -5.0	135.9 (8.5)	-3.5 (5.8); -1.1, -6.0
MADRS						
Exenatide	10.9 (5.1)	8.6 (4.2)	9.0 (4.5)	-1.9 (4.6); -4.1, 0.3	10.2 (6.7)	-0.7 (5.9); -3.5, 2.1
Conventional PD medication	11.0 (5.4)	11.3 (6.5)	11.4 (5.6)	0.5 (4.5); -1.4, 2.4	12.4 (5.6)	1.5 (4.7); -0.5, 3.4
PDQ39 summary index						
Exenatide	19.2 (13.5)	18.1 (13.4)	19.6 (13.0)	0.4 (11.4); -4.9, 5.7	21.5 (19.6)	2.3 (11.6); -3.1, 7.7
Conventional PD medication	24.5 (12.8)	25.2 (15.8)	24.0 (15.3)	-0.6 (11.2); -5.3, 4.2	23.4 (16.0)	-1.2 (9.1); -5.0, 2.7

variables will be performed on the FAS and PP population. The FAS population will serve as the primary population for the analysis of efficacy data. Analyses based on the PP population will be considered as a sensitivity analysis. Subjects will be analyzed for efficacy according to the treatment to which they were randomized.

All safety outcomes will be analyzed using the Safety population. Subjects will be analyzed for safety according to the treatment they actually received.

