Descriptive statistics: The study population will be described using demographic, baseline, and subject characteristics. Descriptive statistics of demographic, baseline, and subject characteristics will be based on the Safety population. A detailed description of subject disposition will include:

- A summary of data on subject discontinuations including reason for withdrawal
- A summary of protocol violations and deviations

All screened subjects will be accounted for in the disposition summaries. The number and percentage of subjects included in each analysis population will be summarized.

Baseline and subject characteristics will include a summary of the following:

- Subject demographics
- Medical history including family history

- Physical examination findings
- Prior and concomitant medications/therapies
- HoMA-IR and QUICKI index at baseline
- MDRS-2 scores at baseline
- MDS-UPDRS scores at baseline
- Non-Motor Symptoms Scale (NMSS) scores at baseline
- PDQ-39 Quality of Life scale scores at baseline
- Delis-Kaplan Executive Function System (DKEFS), Geriatric Depression Scale, and Parkinson's Anxiety Scale scores at baseline

Inferential Statistics on Primary Efficacy Parameter(s): The primary analysis of efficacy endpoint (changes in UPDRS, NMSS, and MDRS-2 scores between baseline and Week 54) will be assessed using a two-sided, two-sample unequal-variance t-test to evaluate the differences in end points between the active and placebo cohorts. Multiple regression analysis will be used for comparisons of between-cohort differences in these outcomes over time. General linear models will be used to evaluate possible associations between baseline characteristics and the primary endpoints. Analysis of covariance (ANCOVA) will be used to evaluate possible effects of peripheral insulin sensitivity and treatment group (independent variables) on the primary end points (dependent variable). Hochberg's method for adjustment for multiple testing separately for the primary end points and secondary endpoints will also be used.

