The last UPDRS, NMSS, and MDRS-2 scores prior to first drug administration will be used as the baseline value in the model and to calculate change from baseline clinical scores. To calculate the change from baseline at week 54, the clinical scores at week 54 will be used. Missing values will be imputed using the last observation carried forward (LOCF) method, including clinical scores on the discontinuation visit. Baseline values will not be carried forward. This methodology will be applied to all treatment groups (liraglutide and placebo).

The assumptions of normality and homogeneity of variance will be explored using probability and residual plots. Data will be tested for normality using the Shapiro-Wilk test. If any of the assumptions are found to be violated, an appropriate transformation of the data or non-parametric test will be considered.

Sensitivity analyses of the primary efficacy endpoint will be performed on the PP population using the same methods described for the FAS population. Summaries of clinical scores, including the change from baseline, will be presented at each visit (i.e., baseline, Week 28, and Week 54). No adjustments have been made to the Type I error rate for the multiple comparisons of the primary or secondary endpoints since this is a phase II study; therefore, results should be interpreted appropriately. No statistical testing within treatment groups will be performed.

Inferential Statistics on Secondary Efficacy Parameter(s): Analyses of secondary efficacy endpoints will be conducted on the FAS and PP populations. The following secondary efficacy endpoints will be analyzed using an approach similar to that described for the primary efficacy endpoints:

- Change in PDQ-39 scores for each domain and total score between baseline and week 54.
- Change in Delis-Kaplan Executive Function System (DKEFS) between baseline and week

- Change in Geriatric Depression Scale between baseline and week 54
- Change in Parkinson's Anxiety Scale scores between baseline and week 54

The safety outcomes of this study will be the following:

- Adverse events
- Serious adverse events
- Clinical laboratory parameters
- Geriatric Depression Scale
- Vital signs
- Physical examination.
- 12-lead ECGs

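### Read plainly, the Full Analysis Set needs follow-up scores on both MDRS-2 and MDS-UPDRS, so a subject with none on one scale leaves every efficacy analysis; define the set per endpoint

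*Combined protocol and SAP*

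**What the plan says.** Statistical Methods defines the FAS as randomised subjects who were dosed and "have a baseline and at least one post-baseline efficacy score (MDRS-2 and MDS-UPDRS". The same section makes the FAS the main efficacy set: "The FAS population will serve as the primary population for the analysis of efficacy data". The per-protocol set is nested in it, as "a subset of the FAS population, excluding subjects with major deviations from the protocol". Efficacy is analysed on these two sets only.

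Three scales are treated as primary in two places. Endpoints lists MDS-UPDRS III together with "non-motor symptoms of PD (assessed by NMSS and MDRS-2) after 52 weeks of treatment", and Inferential Statistics on Primary Efficacy Parameter(s) tests "changes in UPDRS, NMSS, and MDRS-2 scores between baseline and Week 54". The Sample Size Calculation section differs and names one scale: "The primary outcome of this study will be the difference in MDRS-2 scores at baseline and follow-up". NMSS as a primary endpoint therefore rests on the first two sections.

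Missing values are filled by last observation carried forward (LOCF), and scores from a discontinuation visit may be used. The limit is "Baseline values will not be carried forward". The FAS is nowhere defined endpoint by endpoint.

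**The concern.** One analysis set serves separately tested endpoints, and entry depends on two of the scales jointly. Under the plain reading, a subject with MDRS-2 follow-up but no MDS-UPDRS follow-up is lost from the MDRS-2 test on which the trial is powered. A subject with motor and NMSS follow-up but no MDRS-2 follow-up is lost from both of those tests. Observed endpoint data are then discarded because a different scale is missing. This is not the same as a subject with no follow-up on anything, who has no post-baseline data to use.

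At stake are a little power on the MDRS-2, where the placebo arm is small, and an avoidable dispute about who belongs in the primary population. If a scale were missing because the patient had worsened, the exclusion would also depend on outcome.

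**Working it through.** **1. Who is excluded on the plain reading.** Take a dosed subject with valid baselines on all three scales.

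| Any post-baseline MDRS-2 | Any post-baseline MDS-UPDRS | Any post-baseline NMSS | In FAS | Observed data discarded |
|---|---|---|---|---|
| yes | yes | yes | yes | none |
| yes | yes | no | yes | none |
| yes | no | yes | no | MDRS-2, NMSS |
| no | yes | yes | no | MDS-UPDRS, NMSS |

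The second row shows that leaving NMSS out of the condition discards nothing by itself. That subject has no NMSS value to carry forward and would be absent from the NMSS test under a per-endpoint set too. The loss comes from rows three and four.

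**2. How a subject reaches rows three or four.** In the Schedule of events, MDS-UPDRS, MDRS-2 and NMSS are all done at Weeks 28 and 54, the only on-treatment follow-up visits with efficacy scales. A subject scored on both named scales at Week 28 stays in through LOCF whatever happens at Week 54. Exclusion needs one scale obtained at some post-baseline visit and the other at none.

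The likeliest route is withdrawal before Week 28, when entry depends on the discontinuation visit. Withdrawal Criteria asks for a full final evaluation, but its examples of final procedures are safety items and name no efficacy scale, so a partial set of scales is possible. Baselines also come from different visits: MDRS-2 at screening, the other two at the baseline visit.

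**3. Effect on MDRS-2 power.** Inputs from Sample Size Calculation: difference 5.1, SD 6.4 (drug) and 5.3 (placebo), two-sided alpha 0.05, unequal-variance t-test.

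- Standard error: SE = √(6.4²/n₁ + 5.3²/n₂)
- Noncentrality: δ = 5.1/SE
- Degrees of freedom: Satterthwaite
- Power: noncentral t

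The plan's after-dropout figure is reproduced first. With 36 and 15, SE = √(1.138 + 1.873) = 1.735, δ = 2.94, df = 31.5, and power is 81.3%, as stated. (With 38 and 19 the same formula gives 87.6%, not the stated 82.7%, which appears only if the two SDs are swapped. That is a separate matter and is not used here.)

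The documents give no rate of one-scale missingness. I assume zero to two placebo subjects lost because MDS-UPDRS follow-up is absent.

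| Starting case | No loss | One placebo lost | Two placebo lost |
|---|---|---|---|
| 36/15 (plan's dropout split) | 81.3% | 79.3% | 77.1% |
| 34/17 (six dropouts in 2:1 proportion) | 83.7% | 82.2% | 80.5% |

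From 36/15, losing one drug subject gives 80.9%, and one from each arm gives 79.0%.

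These figures concern the MDRS-2 test only. The plan gives no power for MDS-UPDRS or NMSS, so the cost of row four cannot be put as a power figure.

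**The case against.** **The wording.** The clause says score in the singular, so the bracket may simply list which scales count. This stands as an alternative reading, and it means the joint requirement is not certain. It does not remove the need to edit: on that reading a subject may enter with no follow-up on the scale being tested, and FAS membership still depends on who interprets the clause.

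**Reach.** Shared visits, LOCF and the requested final evaluation keep nearly everyone in. This stands. Missing a scale at one visit excludes nobody, and if missingness on the two scales overlaps completely the extra loss is zero.

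**Bias.** A reader might infer that patients who decline until they cannot do the MDRS-2 will be dropped from the motor and NMSS analyses, biasing them. The documents do not establish this. The text on inability, "Concurrent dementia defined by a score lower than 120 on the MDRS-2 and/or inability to complete scale", is a screening exclusion and says nothing about follow-up. The route needs someone testable at screening, untestable at every later assessment, and still scored on the other scales. It is possible but hypothetical.

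**NMSS.** A reader might also infer that the FAS is unusable for NMSS because it omits that scale. It is not, as the second row of the first table shows.

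**Magnitude.** The 36/15 case takes four of 19 from placebo and two of 38 from drug. This stands: power falls below 80% for one or two placebo losses only from that split, not from 34/17.

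**A common set is defensible.** One FAS for all endpoints is simpler to report, and the Hochberg family would rest on one sample. That is a fair preference, but Hochberg's procedure works on the p-values and does not require a common sample.

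**Conclusion.** The point holds as a low-cost improvement. On its plain reading the definition discards observed data on a primary scale when the subject has no follow-up at all on the other named scale; on the alternative reading it is ambiguous. Few subjects, possibly none, are likely to be affected, and early withdrawal with a partial final evaluation is the case most at risk.

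One or two placebo losses would cost about 2 to 4 percentage points of MDRS-2 power from 36/15 (81.3% to 79.3% or 77.1%) and about 1.5 to 3 from 34/17 (83.7% to 82.2% or 80.5%). This rests on the plan's difference and SDs and on an assumed number of losses. The documents do not support a claim of demonstrated bias or of a failed NMSS analysis.

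**What to change.** Replace the single definition with one per endpoint. For each of MDRS-2, MDS-UPDRS and NMSS, the FAS is every randomised, dosed subject with a baseline and at least one post-baseline score on that same scale. Derive the per-protocol set from the matching FAS, and report n per arm for each endpoint. Make the change before unblinding.

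The cost is a short edit to the analysis-set definitions. The n may differ slightly between endpoints, and the per-protocol set and the population counts in the disposition summary must be given per endpoint.

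### The primary test is valid but ignores baseline scores, and the plan refers to a baseline value in a model it never identifies

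*Combined protocol and SAP*

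**What the plan says.** All references are to Statistical Considerations in the combined protocol and SAP.

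The primary comparison of change to week 54 "will be assessed using a two-sided, two-sample unequal-variance t-test to evaluate the differences in end points between the active and placebo cohorts". No covariate is named. The Sample Size Calculation rests on the same test.

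The primary efficacy section then names three models:

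- "Multiple regression analysis will be used for comparisons of between-cohort differences in these outcomes over time". No covariates are listed.
- "General linear models will be used to evaluate possible associations between baseline characteristics and the primary endpoints". Baseline scores could enter here, because Descriptive statistics lists "MDRS-2 scores at baseline", and those of the other scales, among the baseline characteristics. The stated purpose is association, not an adjusted treatment comparison.
- "Analysis of covariance (ANCOVA) will be used to evaluate possible effects of peripheral insulin sensitivity and treatment group". The scale's own baseline score is not listed.

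The section goes on to say that the last scores before first dosing "will be used as the baseline value in the model and to calculate change from baseline clinical scores". It does not say which model.

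**The concern.** A Welch t-test on change has no baseline term, so the remark about a baseline value in a model cannot refer to the primary test. It also mentions that use separately from computing change, so the change score does not explain it. None of the three other models is specified as the treatment effect adjusted for the same scale's baseline. A reader cannot tell whether, where or how such an adjustment will be made.

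The second stake is efficiency. All three scales are scored before the first dose. A change score fixes the coefficient on baseline at 1, whereas ANCOVA estimates it. When the true coefficient is well below 1, the change score carries baseline noise that could be removed. In a trial of 57 patients, that precision would need no new data.

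**Working it through.** **1. The plan's own power figures.** Welch test, two-sided alpha 0.05, difference 5.1, SDs 6.4 (drug) and 5.3 (placebo), noncentral t with Satterthwaite degrees of freedom.

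- 36/15: 81.3%, as the plan states.
- 38/19: 87.6%, against the stated 82.7%. The stated figure appears only if the two SDs are exchanged. This is a separate matter, but the baseline for comparison at 38/19 below is about 88%, not 82.7%.

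**2. Inputs from Table 1, MDRS-2 (SD at baseline / follow-up / of change).**

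- Exenatide: 7.7 / 2.5 / 6.4 at 12 months; 7.7 / 2.0 / 6.0 at 14 months.
- Conventional medication (control): 4.5 / 6.1 / 5.3 at 12 months; 4.5 / 8.5 / 5.8 at 14 months.

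The 12-month change SDs are those used for sizing, and 12 months is closest to the 52-week endpoint.

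**3. Slopes of follow-up on baseline.** Within-arm covariance = (SD0² + SD1² − SDchange²)/2; slope = covariance/SD0².

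- 12 months, exenatide: (59.29 + 6.25 − 40.96)/2 = 12.29; slope 12.29/59.29 = 0.207.
- 12 months, control: (20.25 + 37.21 − 28.09)/2 = 14.685; slope 14.685/20.25 = 0.725.
- 14 months: covariances 13.645 and 29.43; slopes 0.230 and 1.453.

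**4. Common-slope ANCOVA at 38/19, 12 months.** The pooled slope weights each arm by (n − 1)SD0²:

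b = (37×12.29 + 18×14.685)/(37×59.29 + 18×20.25) = 719.06/2558.23 = 0.281.

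Residual variance per arm = SD1² − 2b·cov + b²·SD0²:

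- Exenatide 4.03, against 40.96 for change (down 90%).
- Control 30.55, against 28.09 (up 9%).

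Variance of the treatment difference:

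- Change: 40.96/38 + 28.09/19 = 2.556 (SE 1.599).
- ANCOVA: 4.03/38 + 30.55/19 = 1.714 (SE 1.309).
- Ratio 0.671.

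**5. All cases (variance ratio, ANCOVA / change).** The shared-SD columns keep each arm's slope and residual SD and give both arms the same baseline SD (assumption), as randomisation would lead one to expect.

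| Columns, arm sizes | Pilot SDs | Shared SD 4.5 | Shared SD 7.7 |
|---|---|---|---|
| 12 months, 38/19 | 0.67 | 0.86 | 0.71 |
| 12 months, 36/15 | 0.72 | 0.89 | 0.76 |
| 14 months, 38/19 | 1.03 | 1.13 | 1.25 |
| 14 months, 36/15 | 1.11 | 1.19 | 1.38 |

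At 14 months the control slope exceeds 1, while the pooled slope (0.404 at 38/19) is pulled down by the larger drug arm. The control arm's residual variance rises from 33.64 to 51.76, and it is divided by only 19.

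The pilot arms are small: the Table 1 confidence intervals imply about 20 and 24 patients. Parametric bootstrap 95% ranges for the ratio with pilot SDs are 0.40-0.96 (38/19) and 0.43-1.04 (36/15) at 12 months, and 0.70-1.21 and 0.76-1.32 at 14 months.

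**6. Simulated power for 5.1 points, Welch against HC3 ANCOVA, pilot SDs (20,000 bivariate normal trials per cell).**

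- 12 months: 88% against 96% (38/19); 81% against 90% (36/15).
- 14 months: 85% against 83%; 78% against 72%.

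**7. Type I error, same simulations.**

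- Welch and HC3 ANCOVA: 4.8-5.2%.
- ANCOVA with ordinary equal-variance standard errors: 13-15% (38/19) and 16-19% (36/15). If both arms have the same distribution, about 5%.

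**8. Other primary scales.** Table 1 has no UPDRS or NMSS rows. With equal baseline and follow-up SDs and correlation r, the ratio is (1 − r²)/(2(1 − r)) = (1 + r)/2, or 0.70-0.90 for an assumed r of 0.4-0.8.

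**The case against.** The plan names one primary test, sizes the trial on it, and uses it again in the per-protocol set. The test is valid and unbiased, so replacing it can look like preference. The evidence for a gain changes sign between adjacent columns of Table 1, and the 12-month gain comes wholly from one exenatide arm of about 20 patients whose SD fell from 7.7 to 2.5. For two of the three primary scales there is no evidence in the documents.

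Much of this stands, and it limits the point. Three stronger readings are tempting, but the documents do not support them:

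- *The primary test is wrong or biased.* It is not. Randomisation makes the unadjusted comparison of change valid.
- *The sponsor could choose an adjusted result as primary after seeing the data.* The Welch test is clearly assigned to the primary comparison, so promoting another model would be a visible departure. The looseness lies in the other models and in the one undefined reference.
- *The plan carries a 13-19% false-positive rate.* That figure belongs to an equal-variance ANCOVA under the pilot's variances. The plan does not name that as its primary test, and it says "The assumptions of normality and homogeneity of variance will be explored using probability and residual plots". The figure is only a reason to fix the standard-error method when an ANCOVA is specified.

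The objection leaves two things unanswered. The reference to a model still has no referent. And the columns that supplied the sizing SDs favour adjustment at every shared baseline SD tried from 4.5 to 7.7.

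**Conclusion.** The point holds as a low-cost improvement, not as an error in the primary test. The plan does not specify a baseline-adjusted treatment effect and does not identify the model in which the baseline value is used.

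On the 12-month MDRS-2 data, adjustment would cut the variance of the treatment difference by 28-33% with the pilot's baseline SDs, or by 11-29% with a shared baseline SD. On the 14-month data it would raise it by 3-11%, or by 13-38% with a shared SD. These figures assume one common slope, Table 1 SDs that carry over to liraglutide, and, for power and type I error, normal data. They cover MDRS-2 only. A gain is therefore likely if this trial resembles the pilot at 12 months, but it is not assured. The need to identify the model does not depend on any of these figures.

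**What to change.** Before unblinding, amend the primary efficacy section as follows:

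- For each primary endpoint, prespecify an ANCOVA of the week-54 score on treatment arm and the baseline value of the same scale, with HC3 standard errors.
- State that this is the model in which the baseline value is used.
- Keep the Welch t-test on change as the named sensitivity analysis.
- Name the covariates of the regression over time.
- Apply the same rule to the secondary endpoints, which follow the primary approach.

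Use one common slope. Arm-specific slopes with plain HC3 errors gave simulated type I error of 6.1% (12-month pattern) and 12.5% (14-month pattern) at 38/19.

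The cost is SAP wording and one degree of freedom. The main downside is power on MDRS-2 if the 14-month pattern holds. It would go from about 85% to 83% at 38/19, and from about 78% to 72% with "36 cases in the drug group and 15 cases in the placebo group". If both arms also share a baseline SD of 6.3-6.8 (assumption), it would go from 84-86% to 73-77%, and from 76-78% to 61-64%. The power statement in the Sample Size Calculation applies only to the Welch test and should not be carried over to the ANCOVA.

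If the sponsor will not accept that risk, keep Welch as primary, prespecify the same HC3 ANCOVA as the named supportive analysis, and say that it is the model meant. This removes the ambiguity at no cost to the power of the primary test.
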